11.1.2.1. Statistical Hypotheses for the Primary Safety Endpoint

The statistical hypothesis is that the rate of the primary safety endpoint (composite of all-cause mortality, all stroke, systemic embolization, and major bleeding events evaluated at 6 months after the implant procedure for the WATCHMAN FLX™ Pro device Primary Analysis Subset) is less than a performance goal (PG).

The primary safety endpoint is expressed as the proportion of Primary Analysis Subset subjects who experience mortality, stroke, systemic embolization, and major bleeding events within 6 months after the index procedure among all subjects who either experience mortality/stroke/systemic embolization/major bleeding complications within 6 months after the index procedure or are followed for at least 150 days after the index procedure.

The null and alternative hypotheses for the primary safety endpoint are as follows:

$$H_0: P_{\text{Safety}} \geq PG$$

$$H_1: P_{\text{Safety}} < PG$$

where P_{Safety} is the primary safety endpoint rate for the WATCHMAN FLX Pro Primary Analysis Subset and PG is the performance goal.

The analysis set for the primary safety endpoint is the ITT analysis set from the Primary Analysis Subset. This endpoint will also be analyzed for the implanted analysis set.

A one sample z test will be used to test the one-sided hypothesis of the PG for the WATCHMAN FLX Pro device. If the P value from the z test is <0.025 , the rate of the primary safety endpoint for the WATCHMAN FLX Pro Primary Analysis Subset will be concluded to be less than the PG. This corresponds to the one-sided upper 97.5% confidence bound on the observed rate of the primary safety endpoint at 6 months being less than the PG.

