If new information becomes available that can significantly affect a subject's future health and medical care, that information shall be provided to the affected subject(s) in written form via a revised ICF or, in some situations, enrolled subjects may be requested to sign and date an addendum to the ICF. In addition to new significant information during the course of a study, other situations may necessitate revision of the ICF, such as if there are amendments to the applicable laws, protocol, a change in Principal Investigator, administrative changes, or following annual review by the IRB. The new version of the ICF must be approved by the IRB. Acceptance by Boston Scientific is required if changes to the revised ICF are requested by the site's IRB. The IRB will determine the subject population to be re-consented.

19. Committees

19.1. *Safety Monitoring Process*

The BSC personnel from the Medical Safety and Safety Trial Operation group review safety data as it is reported by the sites throughout the duration of the study. During scheduled monitoring activities, clinical research monitors further support this review through their review of source documents and other data information. The BSC Medical Safety and Safety teams include health care providers with expertise in cardiology and with the necessary therapeutic and subject matter expertise to evaluate and classify the events into the categories outlined above (Section 17).

19.2. *Clinical Events Committee*

A Clinical Events Committee (CEC) will be used in this study. The CEC is an independent group of individuals with pertinent expertise, which reviews and adjudicates important endpoints and relevant adverse events reported by study investigators.

The CEC will review the following events for this study.

- Stroke (disabling and non-disabling; ischemic and hemorrhagic)
- Systemic Embolism
- Pericardial Effusion requiring pericardiocentesis or surgery
- All-cause mortality (cardiovascular and non-cardiovascular)
- Bleeding: ISTH major and non-major clinically significant bleeding including procedural (≤ 7 days post-procedure) and non-procedural (>7 days post-procedure)
- Other events, at the discretion of Boston Scientific

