5.1 Other Endpoints/Measurements

No statistical hypothesis test will be conducted for other endpoints/measurements. The variables of interest will be summarized using descriptive statistics for continuous variables (e.g., mean, standard deviation, n, minimum, maximum) and frequency tables or proportions for discrete variables. The Kaplan-Meier product-limit method will be used to estimate rates for time-to-event endpoints. Adverse event and serious adverse event (SAE) rates will be reported.

Additional endpoints will include the following:

1. CEC-adjudicated:

- Device Success: Defined as implantation of a WATCHMAN FLX Pro device without in-hospital mortality.
- All-cause mortality: Cardiovascular/unknown death and non-cardiovascular death
- All Stroke: Disabling and non-disabling stroke; ischemic and hemorrhagic stroke
- Bleeding: International Society on Thrombosis and Haemostasis (ISTH) major and non-major clinically significant
 - Procedural bleeding and non-procedural bleeding
- Pericardial effusion/tamponade requiring pericardiocentesis or surgery
- Systemic embolism

2. Site reported:

- Device-related thrombus

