7.3 Rules and Definitions

Binary event rates (proportions) will be calculated on a per subject basis.

The number of subjects included in the safety endpoint outcome rates will be based on subjects who have adequate follow-up (see Section **Error! Reference source not found.**) and/or have experienced any CEC-confirmed events.

For baseline categorical variables, “unknown” responses and missing values will not be counted in rate denominators.

The date of last follow-up will be the latest of the following dates for each subject: site-reported adverse event date, CEC-confirmed event date, index procedure date, discharge date, follow-up visit date, and patient withdrawal (defined as: reasons = xx, xx, xx reasons) date from the end of study form.

Days to (event or last known status) = (event or status) date minus procedure date.

Note: subject withdrawal date should always be the last follow-up date and death date should be the subject last follow-up date if the subject didn't withdraw prior to death.

Length of hospital stay = discharge date minus procedure date.

In-hospital event rates are calculated as the proportion of subjects who experience the specified event from index procedure through day of discharge out of all subjects enrolled.

Out-of-hospital event rates are calculated as the proportion of subjects who experience the specified event from the day after discharge through the number of days as specified out of all subjects who were discharged following index procedure and have adequate follow-up or have experienced the event as specified.

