7.4 CEC Binary Event Rates

The calculation method will follow the table below and extend to other endpoints and time points (e.g., 1-year death) with the appropriate modifications to the numbers of days. For example, for 90 days the event must have occurred within 90 days of procedure and the valid data point must be 60 days (early portion of window for the 90-day visit).

The following are the maximum days to event and number of days post-procedure that are adequate follow-up:

Follow-up Visit	Maximum Days to Event*	Days for Adequate Follow-up**
45 Days	45	30
6 Months	180	150
1 Year	365	335

*this is the target date for the follow-up visit except for the 1-year visit where this is the end of the visit window

**this is the start of the visit window

All event rates will be calculated relative to the date of index procedure (i.e., post-procedure).

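### SAP 7.3 drops discharged subjects who die event-free before the adequate-follow-up day, so any out-of-hospital rate of a non-fatal event is biased upward

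*SAP*

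**What the plan says.** SAP 7.3 (Rules and Definitions) sets three denominators for binary event rates.

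- **Safety endpoint rates in general:** subjects with adequate follow-up "and/or have experienced any CEC-confirmed events".
- **In-hospital rates:** events "from index procedure through day of discharge out of all subjects enrolled".
- **Out-of-hospital rates:** events from the day after discharge, "out of all subjects who were discharged following index procedure and have adequate follow-up or have experienced the event as specified".

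Two further rules decide what happens to a death. SAP 7.3 says the "death date should be the subject last follow-up date if the subject didn't withdraw prior to death". SAP 7.4 tabulates the "number of days post-procedure that are adequate follow-up": 30 for the 45-day visit, 150 for 6 months and 335 for 1 year.

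Protocol 19.2 lists all-cause mortality among the events that the Clinical Events Committee (CEC) reviews. Protocol 11.1.2.1 defines the primary safety denominator as subjects who have a component of the composite (death, stroke, systemic embolization or major bleeding) within 6 months "or are followed for at least 150 days after the index procedure".

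**The concern.** A subject who leaves hospital alive and dies on day 120 without a bleed has a complete record for bleeding: none occurred and none can occur. Death is a competing event here, not missing follow-up. The out-of-hospital rule nevertheless handles this subject like one lost on day 120. The rate becomes conditional on having had the event or being followed to the adequate-follow-up day, and it rises as mortality rises. If such rates were tabulated for groups with different mortality, the group with more deaths would show a higher bleeding rate even with the same bleeding.

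The general sentence has the opposite weakness. It keeps the death, but it keeps a subject on any adjudicated event. Someone with a non-major bleed on day 20 who is lost on day 60 would count as stroke-free at 1 year.

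**Working it through.** **1. Reading the rules together.** Take two subjects, both discharged alive and neither with a stroke, in the 1-year stroke rate.

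| Subject | General rule (SAP 7.3) | Out-of-hospital rule (SAP 7.3) |
|---|---|---|
| Dies day 120 | Kept: death is a CEC event | Dropped: last follow-up 120 < 335, no stroke |
| Non-major bleed day 20, lost day 60 | Kept: has a CEC event | Dropped: last follow-up 60 < 335, no stroke |

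The first subject's stroke status is known and the second's is not. The general rule keeps both and the out-of-hospital rule drops both. The second subject would also be outside the protocol's 6-month primary safety denominator: there is no composite component and there are fewer than 150 days of follow-up.

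**2. The plan's own figure, for scale.** The documents state no figure for out-of-hospital rates. The primary safety sample size does reproduce: 500 × (1 − 0.03) = 485 evaluable. For 14% against a goal of 21% at one-sided 0.025, power with the null variance is Φ[((0.21 − 0.14)√485 − 1.96√(0.21 × 0.79)) / √(0.14 × 0.86)] = 98.4%. With the alternative variance it is 99.3%. Both satisfy the stated >95%.

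**3. Direction.** Let N be the number discharged alive, E those with the event, and D those who die event-free before the adequate-follow-up day, with no other loss. The written rule gives E/(N − D). Keeping deaths gives E/N. The ratio is 1/(1 − D/N), which exceeds 1 whenever D > 0.

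**4. Illustration with 500 discharged and 25 events (assumed counts).** Deaths kept: 25/500 = 5.00%.

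| Event-free early deaths D | Written rule | Excess (points) |
|---|---|---|
| 10 | 25/490 = 5.10% | 0.10 |
| 15 | 25/485 = 5.15% | 0.15 |
| 25 | 25/475 = 5.26% | 0.26 |

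**5. A ceiling at 6 months.** Consider an event that is a component of the composite. Suppose the event proportion b and the event-free death proportion d together equal the plan's expected 14%, and that every such death falls after discharge and before day 150. The excess b·d/(1 − d) is then largest at d = 7.26%, b = 6.74%: 7.27% instead of 6.74%, or 0.53 point. With the 21% goal as the cap it is 1.24 points.

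**6. Simulation with constant hazards.** All rates are assumptions. The first four rows are at 1 year (day 365, adequate follow-up day 335) with 5% loss. The last is at 6 months (day 180, adequate day 150) with 3% loss. The true proportion is the cumulative incidence with death as a competing event.

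| Event, mortality | True | Written rule | Deaths kept | Due to dropped deaths | Due to early loss |
|---|---|---|---|---|---|
| Bleed 10%, death 5% | 9.74% | 10.39% | 9.93% | 0.46 | 0.19 |
| Bleed 10%, death 8% | 9.61% | 10.54% | 9.79% | 0.75 | 0.18 |
| Bleed 10%, death 10% | 9.47% | 10.58% | 9.64% | 0.94 | 0.17 |
| Stroke 3%, death 8% | 2.88% | 3.17% | 2.93% | 0.24 | 0.05 |
| 6 months: bleed 6%, death 4% | 5.89% | 6.15% | 5.94% | 0.21 | 0.05 |

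The fifth column is written rule minus deaths kept; the sixth is deaths kept minus true. With 1,000 subjects the standard deviation of the 1-year bleeding estimate is about 0.95 to 1.04 points, so the death effect is roughly half to one standard error. A re-run with 3 million subjects gave the same death effects to within 0.01 point.

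**7. Against a Kaplan-Meier target.** At 6 months without loss, a 5% event risk and 3% death risk give 5.06% under the written rule, against a cumulative incidence of 4.93% and a Kaplan-Meier target of 5.00%. At 8% and 5% the figures are 8.13%, 7.80% and 8.00%. The rule is too high on either standard.

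**The case against.** The strongest case against is about importance.

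- **No scheduled use.** Out-of-hospital rates are defined once, in SAP 7.3. They are not among the additional endpoints in Protocol 6.2 or SAP 5.1, and Protocol 6.2 splits bleeding at 7 days, not at discharge. A reader might infer from SAP section 5 that these rates will be reported for all four subsets. The documents do not say so: that section applies its own analyses to the subsets, not the definitions in section 7. This stands.
- **No test is touched.** A reader might infer that the primary safety result is biased too. Dropped deaths cannot do that, because death is a component of the composite and keeps the subject in the denominator. SAP 5.1 plans no test for the other endpoints. The error also overstates harm and cannot flatter the device. This stands.
- **The whole excess is not due to deaths.** In the 1-year bleeding examples the total excess is 0.65 to 1.1 points, but about 0.2 of that comes from early loss and would survive the fix. The examples also count every bleed as out-of-hospital, so 10% is probably high for this rate. This stands.
- **Different periods need different risk sets.** True, and a discharged-only set is reasonable for an out-of-hospital rate. It does not explain why a death counts as complete information under one rule and not under the other.
- **Other provisions help.** SAP 5.1 states: "The Kaplan-Meier product-limit method will be used to estimate rates for time-to-event endpoints". SAP 7.2 allows adjustment for missing outcomes if judged necessary. Neither changes the out-of-hospital proportion, and the outcome of a subject who has died is not missing.

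**Conclusion.** The point holds in a limited form. Followed exactly, SAP 7.3 removes subjects with known outcomes from the out-of-hospital denominator and so overstates any out-of-hospital rate of a non-fatal event. The direction is arithmetic and needs no assumption beyond at least one such death and one event.

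The size does rest on assumptions, since the documents give no component or death rates: about 0.5, 0.75 and 0.95 points at 1 year for 10% bleeding, 5% loss and 5, 8 and 10% mortality, and about 0.2 point at 6 months. Only deaths after discharge and before day 30, 150 or 335 contribute.

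The general sentence needs the matching correction, because it keeps early losses on the strength of an unrelated event and so departs from Protocol 11.1.2.1. That departure was not quantified. This is a correction to a descriptive definition, worth making before analysis, and not a threat to either primary conclusion.

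**What to change.** In SAP 7.3, define the out-of-hospital denominator as: *all subjects discharged alive who experienced the specified event after discharge and by day X, or died by day X, or have adequate follow-up for day X*.

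In the general safety-rate sentence, replace the condition on any CEC-confirmed event with the same three-part condition: specified event, or death, or adequate follow-up. For the 6-month composite this gives the denominator of Protocol 11.1.2.1, because death is already a component.

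Both rates then treat deaths by one rule. A reader might expect the out-of-hospital and overall tables to match after this. They will not, because in-hospital events and in-hospital deaths stay outside the discharged set. Bias from early loss to follow-up also remains and needs its own handling.

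The cost is two SAP sentences and a small change to the denominator code, with no new data. SAP 5.6 already provides for an amendment approved before the analyses are run.

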7.4 CEC Binary Event Rates

The calculation method will follow the table below and extend to other endpoints and time points (e.g., 1-year death) with the appropriate modifications to the numbers of days. For example, for 90 days the event must have occurred within 90 days of procedure and the valid data point must be 60 days (early portion of window for the 90-day visit).

The following are the maximum days to event and number of days post-procedure that are adequate follow-up:

Follow-up Visit	Maximum Days to Event*	Days for Adequate Follow-up**
45 Days	45	30
6 Months	180	150
1 Year	365	335

*this is the target date for the follow-up visit except for the 1-year visit where this is the end of the visit window

**this is the start of the visit window

All event rates will be calculated relative to the date of index procedure (i.e., post-procedure).

7.5 Summarization of Site-Reported Serious and Non-Serious Adverse Events

Site-reported subject-based event rates will be calculated at various time points based on all events reported by the site. All enrolled subjects will be included in the analyses.

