16.5. Anticipated Benefits

The clinical benefit of the WATCHMAN FLX Pro LAA Closure Device is to decrease the risk of stroke by preventing thrombus embolization from the left atrial appendage and decrease the risk of major bleeding events by reducing the need for long-term blood thinners in patients with non-valvular atrial fibrillation.

There may also be economic and subject benefits related to the elimination of life-long compliance to anticoagulation therapy and the frequent blood tests and lifestyle changes associated with blood thinning medications.

17. Safety Reporting

17.1. *Reportable Events by investigational site to Boston Scientific*

For enrolled subjects, it is the responsibility of the investigator to assess and report to BSC any event which occurs from the beginning of the Index Procedure through 12-month follow-up visit for all subjects including any of following categories:

- All Serious Adverse Events (SAE) regardless of cause – see **Note 1** below
- Adverse Events (AE) related to the WATCHMAN FLX Pro device and/or WATCHMAN FLX Pro implant procedure
- Unanticipated Adverse Device Effects (UADE) / Unanticipated Serious Adverse Device Effects (USADE)
- Adverse Event where systemic embolism is suspected and/or confirmed, regardless of relationship to the WATCHMAN FLX Pro device
- All bleeding events regardless of relationship to the WATCHMAN FLX Pro device
- All strokes (regardless of cause) and transient ischemic attacks (TIAs) regardless of relationship to the WATCHMAN FLX Pro device
- New findings/updates in relation to already reported events
- Device Deficiency

Note 1: Planned hospitalization for a pre-existing condition, or a procedure required by the clinical investigational plan, without serious deterioration in health, is not considered a serious adverse event. Changes to the planned date of procedure/hospitalization are permitted and will not trigger event reporting.

When possible, the medical diagnosis should be reported as the Event Term instead of individual symptoms.

If it is unclear whether or not an event fits one of the above categories, or if the event cannot be isolated from the device or implant procedure, it should be submitted as an adverse event and/or device deficiency.

Any reportable event, experienced by the study subject after informed consent and once considered enrolled in the study (as defined in Section 9.1), whether prior to, during or subsequent to the study procedure, must be recorded in the eCRF.

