5.5 Other Analyses

Administrative analyses of safety data may be performed for regulatory agency review. Descriptive statistics of subject demographic, baseline characteristics, procedure characteristics, medical history will be presented for each analysis subset. the overall study population

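### SAP 7.5 computes site-reported AE and SAE rates over all enrolled subjects with no follow-up condition or censoring, so they are biased low: slightly in the final report, substantially only if applied before follow-up is complete

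*SAP*

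**What the plan says.** SAP 7.5 consists of two sentences. Subject-based rates are to be calculated at several time points, "based on all events reported by the site. All enrolled subjects will be included in the analyses". Section 7.3 makes binary event rates per-subject proportions, so the natural reading is events divided by everyone enrolled. The time points are not listed.

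Other rates follow a different rule:

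- **Safety endpoint rates (SAP 7.3):** "The number of subjects included in the safety endpoint outcome rates will be based on subjects who have adequate follow-up", or who had a CEC-confirmed event.
- **Out-of-hospital rates (SAP 7.3):** the denominator is discharged subjects who "have adequate follow-up or have experienced the event as specified".
- **CEC rates (SAP 7.4):** the table introduced by "The following are the maximum days to event and number of days post-procedure that are adequate follow-up" sets 30, 150 and 335 days for the 45-day, 6-month and 1-year rates.
- **In-hospital rates (SAP 7.3):** all enrolled subjects, which is reasonable because each is observed to discharge.

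SAP 5.1 plans Kaplan-Meier estimates for time-to-event endpoints, then says in a separate sentence, without a method, that AE and SAE rates will be reported. SAP 7.2 allows models for censored data where appropriate. Neither is tied to 7.5. SAP 5.5 adds: "Administrative analyses of safety data may be performed for regulatory agency review". It gives no data-cut rule.

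**The concern.** A rate at 6 or 12 months should describe risk over that period. Under 7.5, a subject who withdrew at month 2 stays in the denominator of the 12-month rate. Protocol 9.2 stops data collection at withdrawal, so that subject's later events can never enter the numerator. The same holds for a subject still in follow-up at a data cut. The rule pulls the rate in one direction only. Keeping subjects who died in the denominator is correct; the fault concerns those who left or are still being followed.

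Two things are at stake. Protocol 7.3 says the data are meant to support regulatory submissions, so an SAE rate that is low for reasons unrelated to the device matters. Also, strokes and bleeds are reportable by sites (Protocol 17.1), and strokes and clinically significant bleeds are reviewed by the CEC as well (Protocol 19.2). One report could thus show two rates for the same kind of event on different denominators, without explanation.

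**Working it through.** **The plan's own figure.** Section 7.5 states none. The nearest is the safety attrition in the SAP summary: 485 evaluable subjects at 3% attrition gives 485 / 0.97 = 500, which reproduces. That 3% belongs to the 6-month endpoint; no 12-month figure is given.

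**Inputs from the documents.** Accrual about 6 months; follow-up 12 months per subject; attrition 3%.

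**Assumptions.** Uniform accrual; constant hazard; 12-month risk 30% (checked at 20% and 40%); exits spread evenly over 12 months and unrelated to risk; no dropout in the data-cut scenarios.

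Hazard: λ = −ln(0.7) / 12 = 0.02972 per month. True risk: 30% at 12 months and 1 − exp(−6λ) = 16.3% at 6 months.

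**Final report, 12-month rate.** A subject who exits has an event observed before exit with mean probability 1 − (1 − 0.7) / (12λ) = 1 − 0.3 / 0.3567 = 0.1589.

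- 3% attrition: 0.97 × 0.30 + 0.03 × 0.1589 = 0.2958, or −1.4% relative.
- 10% attrition (assumed): 0.90 × 0.30 + 0.10 × 0.1589 = 0.2859, or −4.7%.

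**Conditional illustration: 7.5 applied at an early cut.** With entry time e uniform on 0 to 6 months and a cut at month c, the all-enrolled rate at time t is the mean over e of 1 − exp(−λ × min(c − e, t)).

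Month-9 cut, 12-month rate: follow-up runs uniformly from 3 to 9 months, so the rate is 1 − [exp(−3λ) − exp(−9λ)] / (6λ) = 1 − (0.9147 − 0.7653) / 0.1783 = 16.2%.

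| Cut | Rate | All enrolled | True | Relative error |
|---|---|---|---|---|
| Month 9 | 6-month | 14.4% | 16.3% | −12% |
| Month 9 | 12-month | 16.2% | 30% | −46% |
| Month 12 | 12-month | 23.4% | 30% | −22% |
| Month 15 | 12-month | 28.4% | 30% | −5% |

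At assumed 12-month risks of 20% and 40%, the month-9 error in the 12-month rate is −47% and −44%. A different hazard, set to give 14% at 180 days, leads to the same conclusion: at a day-270 cut the 12-month rate is 13.9% against 26.4%, or 53% of its true value.

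**Would borrowing the SAP 7.4 denominator help?** Counting only subjects with the event or with adequate follow-up, on the same model:

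| Cut | Rate | Event or adequate follow-up | True |
|---|---|---|---|
| Month 9 | 6-month | 20.2% | 16.3% |
| Month 9 | 12-month | 100% | 30% |
| Month 12 | 12-month | 66.5% | 30% |

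At month 9 nobody has 335 days of follow-up, so only subjects with events remain in the 12-month denominator. At these cuts this rule overstates by more than 7.5 understates.

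**The case against.** The strongest reply is that the large figures describe an analysis the SAP does not specify. Section 5.5 says only that administrative analyses may be done. It does not say that they use 7.5 or that they report time points not yet reached. No formal interim analysis is planned, and at month 9 no subject has 12 months of follow-up, so a rate labelled as 12-month would be hard to defend. This stands. A reader might infer that regulators will be shown SAE rates cut roughly in half; the documents do not support that.

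Crude AE incidence over all enrolled subjects is also a common descriptive summary, and no hypothesis test rests on it. That too is fair. The fault is in presenting the proportion as a rate at a time point.

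The Kaplan-Meier and censored-data provisions in SAP 5.1 and 7.2 soften the point but do not answer it, because nothing links them to 7.5, which states its own rule.

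A reader might also infer that the numerator is defective. Protocol 17.1 makes non-serious events reportable only in certain categories, such as "Adverse Events (AE) related to the WATCHMAN FLX Pro device and/or WATCHMAN FLX Pro implant procedure", so a total for non-serious events would be incomplete. But the SAP's reference to events reported by the site reads naturally as those reportable events, and it promises no count of every non-serious AE. This is a matter of labelling.

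Finally, the contrast with SAP 7.4 shows that the denominators differ. It does not make 7.4 the right benchmark at an early cut.

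**Conclusion.** The point holds. On its plain reading, SAP 7.5 treats unobserved follow-up as event-free and biases site-reported rates downward. The direction does not depend on the assumptions; the size does.

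For the final report the bias is small: about 1.4% relative on a 12-month rate at 3% attrition, 4.7% at 10%. The 3% is carried over from the 6-month endpoint, and the 30% risk and the 10% are assumed. The larger errors (46%, 22% and 5% at months 9, 12 and 15) arise only if a SAP 5.5 analysis applies 7.5 before follow-up is complete. They also rest on a constant hazard; if events cluster around the procedure, the shortfall would be smaller.

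It would be wrong to conclude that the primary results are at risk. The efficacy endpoint uses subjects with a core-lab 45-day TEE, and the safety endpoint and CEC rates have their own follow-up rule. This is a reporting fault worth correcting, with no bearing on the study's hypothesis tests.

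**What to change.** Replace the second sentence of SAP 7.5. For any site-reported rate at a post-discharge time point, report the cumulative incidence with censoring at last follow-up (already defined in SAP 7.3) and death as a competing event, and show the number at risk. For an any-SAE rate a fatal SAE counts as the event, so the competing-event treatment matters mainly for specific event categories. State that the rule also applies to administrative analyses under SAP 5.5. A crude count over all enrolled subjects may stand beside it if labelled as such.

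Do not carry the event-or-adequate-follow-up denominator into early cuts, because it overstates the rate.

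Optionally, label the non-serious AE table as covering only the categories reportable under Protocol 17.1.

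The cost is a short SAP amendment and slightly more, though standard, programming. No new data are needed. The sponsor should expect slightly less favourable rates in the final report.
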